## 3. Procedure

The control group carried out normal perioperative and chemotherapy nursing process, while the intervention group used upper limb lymphedema prevention program to manage patients. The specific implementation process was as follows:

Coming for surgery: 1. A PPT lecture; 2. A seminar; 3. Patients were given a lymphedema prevention brochure; 4. Diary cards for exercise is given and instruct patients to fill out daily; 5. Establish a WeChat group.

The first chemotherapy: 1. Review diary card and provide guidance and education. 2. A PPT lecture; 3. A seminar; 4. Play functional exercise videos in the recovery room; 5. Rehabilitation volunteers come to the ward to form mutual help groups with patients under the guidance of subject team members; 6. Instruct regular exercise and avoid behaviors that can lead to lymphedema. 7. Ask about the exercise and whether there is any swelling and discomfort and give guidance.

The second chemotherapy: 1. A PPT lecture; 2. A seminar; 3. Play functional exercise videos in the recovery room.

The third chemotherapy: 1. Routine nursing; 2. Assess patients' knowledge of

lymphedema prevention and exercise compliances; 3. Play functional exercise videos in the recovery room.

### 3.1 Data collection

The data collection personnel were trained uniformly, and the collection personnel were not aware of the grouping of patients. Before the intervention, the whole process of the prevention program, its purpose and significance were explained to the patients in detail, and the patients were asked to fill in the informed consent form, telling the patients that they had the right to withdraw from the trial at any time.

Considering the compliance of patients in the survey, this study collected data from patients at three time periods. The baseline data of patients before intervention were collected in stage 1 (T0), stage 2 (T1) was the third time for chemotherapy (21 days as a chemotherapy cycle), and stage 3 (T2) was the sixth time for chemotherapy.

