## Research Proposal

### 1 INTRODUCTION AND BACKGROUND

With an estimated 19.3 million new cancer cases worldwide in 2020, breast cancer in women overtook lung cancer as the most common cancer for the first time. Surgery is the most commonly used treatment for Breast Cancer, but it can lead to some complications, such as wound bleeding, infection, subcutaneous effusion, flap necrosis, limb dysfunction and Breast cancer-related Lymphedema (BCRL). Among them, BCRL can lead to upper limb dysfunction, muscle weakness, appearance impairment, anxiety and depression and other physical and psychological problems in breast cancer patients, which seriously affect the postoperative rehabilitation and quality of life of patients, and BCRL is difficult to cure once it occurs. According to relevant literature reports, the incidence of BCRL is about 21.4%, which is a widespread problem.

BCRL is due to a variety of breast cancer treatment methods damage the lymphatic system, resulting in lymphatic vessel fracture and morphological changes in the affected limb, so that the lymphatic fluid can not smoothly return, so that the affected arm of patients with swelling and pain, severe cases will cause infection and tissue fibrosis. At present, physical treatment, drug treatment or surgery can improve edema symptoms in different degrees, but due to the longer course of treatment, high cost, difficult lasting effect and other problems, so that many patients can not adhere to the treatment. BCRL has been recognized as a difficult point in the rehabilitation of patients, and medical workers need to pay attention to it.

Due to the lack of understanding of lymphedema in most patients, the initial manifestations of BCRL are easy to be ignored by patients, resulting in difficulties in the early prevention and detection of edema. Some domestic studies investigated local patients with the knowledge of lymphedema prevention after breast cancer surgery, and the results showed that the patients had a poor grasp of relevant knowledge, with an average score rate of 25.18%, which was significantly lower than the international median awareness rate of lymphedema. Since BCRL is difficult to cure once it occurs, researchers pay more and more attention to the prevention and early intervention of lymphedema, and improve the awareness and education of patients about the risk of lymphedema, which has become a necessary measure to improve the quality of life of breast cancer patients.

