At present, knowledge, attitude and practice theory is widely used in rehabilitation guidance and education of patients. Based on KAP theory and combined with the best evidence of upper limb lymphedema prevention in patients after breast cancer surgery, this study plans to formulate a prevention plan for upper limb lymphedema in patients after breast cancer surgery, and apply this plan in clinical practice, so as to improve patients' cognition of lymphedema and promote patients to master and take positive rehabilitation behaviors. So as to reduce the incidence of upper limb lymphedema, improve the grip strength and function of the affected upper limb, and improve the quality of life of patients.

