## 2.3 Power analysis

This study used PASS 15.0 to calculate the sample size, using two-sided test,  $\alpha = 0.05$  and  $1 - \beta = 0.8$ . According to the literature,  $P_1$  was taken as 30% and  $P_2 = 5\%$ . The final calculation yielded  $N_1 = N_2 = 44$ , considering the 20% loss to follow-up rate after surgery, and the final total sample size was set at 106 cases, with 53 cases in the intervention group and 53 cases in the control group.

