## 2.4 Randomization

The unit admitting breast cancer was divided into four medical groups, whose members had been trained in homogeneous surgical operations. As each medical group managed fixed patients and wards, patients in different medical groups were treated in different wards. To avoid contamination between the intervention and control groups, the study was conducted in regional randomized groups based on departmental medical groups (block size is 4). Four labels were placed in four opaque envelopes, two with 0 and the other two with 1. Four physicians representing their respective groups drew the envelopes, and the patients enrolled in the two medical groups with "0" were designated as the control group, while the other two groups were designated as the intervention group.

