#### 3.2.1 Assessment of upper limb edema on the affected side:

using an inelastic flexible ruler, the circumference of the wrist was measured at five locations: flat wrist stripes, 10cm, 20cm, 30cm and 40cm above the wrist stripes. The upper limb could be divided into four truncated cones, and the measurement value was accurate to 0.1cm. The upper arm volume can be obtained by using the formula, where  $\pi = 3.14$ , each h is 10 cm, C1 and C2 are the circumference of the two measuring points immediately adjacent to each other, and then the upper arm volume is obtained by adding up the limb volumes at several locations. According to the International Society of Lymphatics, a volume difference of 10% or more is defined as lymphedema, less than 20% as mild lymphedema, 20% to 40% as moderate lymphedema, and more than 40% as severe lymphedema.

Secondary outcome measures:

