#### 4 Data analysis

SPSS21.0 software was used, a two-sided test was set, and  $\alpha$  was set at 0.05. The normality of measurement data was expressed as mean  $\pm$  standard deviation ( $\pm s$ ), and two independent sample t-test was used. When not normal, the median and interquartile range [M(Q)] were expressed using the Mann-Whitney U test. Enumeration data were expressed as frequency and constituent ratio using 2 test. Mann-whitney U test was used for grade data.

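### Does the lack of a named primary visit (T1 or T2) for lymphedema inflate the false-positive rate of the primary comparison?

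*Protocol*

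**What the plan says.** Section 1 of the protocol gives the aim as to "reduce the incidence of upper limb lymphedema", without saying how incidence is counted. Section 3.2.1 is the only primary outcome. It derives arm volume from circumferences and states that "a volume difference of 10% or more is defined as lymphedema"; it names no visit.

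Section 3.1 sets the schedule: "this study collected data from patients at three time periods". T0 is baseline, T1 is the third chemotherapy, and "stage 3 (T2) was the sixth time for chemotherapy". It ranks neither post-baseline visit above the other.

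Section 2.3 opens with "This study used PASS 15.0 to calculate the sample size" and gives one calculation: two-sided alpha 0.05, power 0.8, P1 = 30%, P2 = 5%, 44 per arm, raised to 53 per arm. It does not label the two rates. That they are lymphedema proportions is an inference from sections 1 and 3.2.1.

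Section 4 says "SPSS21.0 software was used, a two-sided test was set" with alpha 0.05. It gives no rule for repeated visits and does not say whether the chi-square is continuity-corrected.

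**The concern.** One alpha of 0.05 and one power of 80% belong to one test. The text can be read as permitting three primary results: the proportion with lymphedema at T1, the proportion at T2, or the proportion with any onset by T2. If a significant difference at either visit could be claimed as success, there would be two chances at the full 0.05 where the sample size allows for one.

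The definition also affects what is estimated, since presence at T2 and onset by T2 differ whenever some T1 cases resolve. Section 5 reports that follow-up is complete for 97 patients, so a choice made only now could in principle be made with results in view. At stake is the meaning of the primary p-value.

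**Working it through.** **Inputs.** Alpha 0.05 two-sided, power 0.8, 30% and 5%, 44 then 53 per arm (section 2.3); 50 control and 47 intervention completers (section 5); two post-baseline visits (section 3.1); a literature incidence of 21.4% (section 1). The documents give no T1–T2 correlation, so it is assumed and varied.

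**The plan's own figure.** The mean rate is (0.30 + 0.05)/2 = 0.175. The pooled formula gives

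n = [1.96·√(2·0.175·0.825) + 0.8416·√(0.30·0.70 + 0.05·0.95)]² / 0.25² = 35.06, so 36 per arm.

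With continuity correction, n' = (n/4)·[1 + √(1 + 4/(n·0.25))]². Starting from 35.06 this is 42.68, so 43. Starting from the rounded 36 it is 9·(1 + √1.4444)² = 43.63, so 44. The stated 44 is therefore what one corrected comparison at 0.05 requires. The step to 53 is 44 × 1.2 = 52.8.

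**Ceiling if either visit may count.** Two independent tests at 0.05 give 1 − 0.95² = 0.0975, which is 1.95 times 0.05. With correlation r between the two test statistics (bivariate normal), the rate is:

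| r | either visit |
|---|---|
| 0 | 9.75% |
| 0.5 | 9.1% |
| 0.7 | 8.4% |
| 0.9 | 7.0% |
| 1 | 5.0% |

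**Simulation on yes/no data.** No true effect, 50 versus 47 independent patients, at least 200,000 runs per setting. In the first setting prevalence is the same at both visits (17.5%, 21.4% or 30%) and the yes/no correlation runs from 0 to 0.95. In the second every T1 case is still a case at T2, and T1 prevalence is 25% to 90% of T2 prevalence. Repeat runs differ by 0.1 to 0.2 percentage points.

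| Setting | Uncorrected chi-square | Continuity-corrected |
|---|---|---|
| One visit, equal prevalence | 4.9–5.2% | 2.5–3.0% |
| Onset by T2, equal prevalence | 4.6–5.2% | 2.6–3.0% |
| Either visit, equal prevalence | 6.3–10.2% | 3.4–5.9% |
| Either visit, all T1 cases persist | 6.7–9.4% | 3.0–4.7% |

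If onset by T2 is added as a third permitted route, the uncorrected rate reaches about 12.1% at its highest.

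**How plausible the ceiling is.** At 21.4% prevalence, zero correlation means that 1 − 0.214 = 79% of T1 cases are no longer cases at T2. Section 1 says "BCRL is difficult to cure once it occurs". With equal prevalence and 87% to 96% of T1 cases persisting, the uncorrected rate is about 6.4% to 7.8%.

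**Whether the case definition matters.** At zero correlation, onset by T2 would be 1 − 0.786² = 38%, against 21.4% at a single visit. At correlation 0.95 the share affected at both visits is 0.214² + 0.95·0.214·0.786 = 0.206, and onset by T2 is 2·0.214 − 0.206 = 22%. If every T1 case persists, the two definitions coincide. Section 2.2 excludes patients with edema of the affected limb before surgery, so any later case is a new one.

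**Which visit the text points to.** Section 2.2 requires six or more planned chemotherapy cycles, so T2 is a visit every eligible patient is meant to reach, and it ends the measurement schedule. T1 falls at the last programme step listed in section 3. An aim stated as reduced incidence, with a lasting condition and no cases at entry, reads most naturally as cases by the end of follow-up.

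**The case for a change.** The strongest case for acting is that the time point and the case definition are part of what a primary outcome is, and are not detail to leave to an analysis plan. This protocol has outcome, sample-size and analysis sections, and none of them fixes either. The figures reproduce. Even with persistent cases, an uncorrected chi-square with free choice of visit gives 6.7% to 9.4%, and section 4 does not rule that version out. Two or three sentences would settle it.

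Much of this stands: a reader has to infer the primary visit, and a report of the trial should say which visit was used and when that was decided. What does not stand is the step from silence to inflation. Section 3.1 describes a collection schedule and contradicts nothing. No section says that success at either visit counts, and section 2.3 gives one comparison at one alpha. Nor can naming a visit after follow-up has ended restore prespecification; only disclosure would be left. Section 5 reports participant counts and no outcomes, so it is no evidence that a choice was made with results known, and an analysis plan not seen here may record the choice.

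All the error rates assume independent patients. Section 2.4 says "the study was conducted in regional randomized groups based on departmental medical groups", with two medical groups per arm. That is a separate question, and naming a visit would not answer it.

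**Conclusion.** The primary outcome lacks a stated visit and a counting rule, but the protocol sets no rule that yields a wrong result. The inflation, about 6.3% to 10.2% uncorrected or 3.0% to 5.9% corrected, arises only if either visit is allowed to count, which the text nowhere grants. Its upper end needs T1 and T2 status to be nearly unrelated. With persistent cases and the corrected test that matches the stated sample size, the rate is 3.0% to 4.7% even with both visits in play. A single test at T2, or of onset by T2, keeps its level under either version (at most about 5.2%), and the two are the same proportion if cases persist.

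This rests on independent patients, on P1 and P2 being lymphedema proportions, and on assumed correlations. The gap is one that an analyst fills sensibly with T2 and reports openly. No change to the plan follows.

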### 3.2 measures

Primary outcome measures:

#### 3.2.1 Assessment of upper limb edema on the affected side:

using an inelastic flexible ruler, the circumference of the wrist was measured at five locations: flat wrist stripes, 10cm, 20cm, 30cm and 40cm above the wrist stripes. The upper limb could be divided into four truncated cones, and the measurement value was accurate to 0.1cm. The upper arm volume can be obtained by using the formula, where  $\pi = 3.14$ , each h is 10 cm, C1 and C2 are the circumference of the two measuring points immediately adjacent to each other, and then the upper arm volume is obtained by adding up the limb volumes at several locations. According to the International Society of Lymphatics, a volume difference of 10% or more is defined as lymphedema, less than 20% as mild lymphedema, 20% to 40% as moderate lymphedema, and more than 40% as severe lymphedema.

Secondary outcome measures:

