## 2.2 Sample

Inclusion criteria: (1) Female patients were  $\geq 18$  years old; (2) Pathological puncture confirmed breast cancer with unilateral, no recurrence, and no metastasis; (3) Patients with clinical TNM stage I ~III; (4) Patients with proposed surgery and 6 or more chemotherapy; (5) The patient was conscious and aware of his condition, with no cognitive impairment or communication problems. Exclusion criteria: (1) Patients who had cancer other than breast cancer; (2) Patients who had history of arm or neck trauma, infection or surgery; (3) Patients who had serious diseases such as cardiovascular, cerebrovascular, liver, kidney, etc; (4) Patients who had upper limb disability or the affected limb has edema before surgery; (5) Patients who had thrombus in the blood vessels of the affected limb.

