#### 5 RESULTS

In this study, a total of 108 patients completed the baseline survey (T0), 56 in the control group and 52 in the intervention group. A total of 11 patients fell off during the study (6 in the control group and 5 in the intervention group), and a total of 97 patients completed the study (50 in the control group and 47 in the intervention group), as shown in Figure 1.

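### Does the 10% lymphedema rule need a new definition because its comparator is not written down?

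*Protocol*

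**What the plan says.** Protocol section 3.2.1, headed "Assessment of upper limb edema on the affected side", holds the only primary outcome. Circumferences are taken at five points, and four truncated cones are summed to a limb volume. In the formula's legend "C1 and C2 are the circumference of the two measuring points immediately adjacent to each other", which describes one limb. The rule is then introduced with "According to the International Society of Lymphatics" and stated as "a volume difference of 10% or more is defined as lymphedema", with grade limits at 20% and 40%.

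The rest of the protocol does not name a comparator:

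- Section 2.2 admits unilateral disease only and excludes "Patients who had upper limb disability or the affected limb has edema before surgery", without a volume limit.
- Section 3.1 sets a baseline visit (T0) before the intervention and follow-up at the third (T1) and sixth (T2) chemotherapy. It does not say which arms are taped or tie T0 to the 10%.
- Section 4 names tests only, among them "Mann-whitney U test was used for grade data".
- Section 5 reports that "a total of 97 patients completed the study".

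**The concern.** A difference needs two quantities, and section 3.2.1 describes one. Two simple readings are possible. Against the same arm at T0, any general change in limb volume (weight, fluid) counts as swelling. Against the other arm without baseline correction, natural asymmetry present before surgery adds to the swelling or hides it. The exclusion in section 2.2 concerns edema, so ordinary asymmetry below 10% stays in.

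The stake would be the primary result. The sample size in section 2.3 rests on event proportions of 30% and 5%, and the reading decides which patients near the threshold are events. The 20% and 40% grades would move in the same way, if they are the graded data that section 4 has in mind; it does not name them.

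**Working it through.** **1. The plan's own figure.** Inputs from section 2.3: P1 = 0.30, P2 = 0.05, two-sided α = 0.05, power 0.80. With d = 0.25 and a pooled proportion of 0.175:

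n = [1.960·√(2·0.175·0.825) + 0.842·√(0.30·0.70 + 0.05·0.95)]² / 0.25² = 35.1, so 36.

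Continuity correction: (35.1/4)·[1 + √(1 + 4/(35.1·0.25))]² = 42.7, so 43. The stated 44 per group is reproduced to within one, so the concern does not rest on a sample-size error.

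**2. How far the readings diverge.** A uniform rise in circumference of √1.10 − 1 = 4.9% gives 10% volume. Let d now be the general change (same-arm reading) or the prior asymmetry (between-arm reading). The true swelling needed to count is 1.10/(1 + d) − 1:

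| d | +3% | +6% | +9% | −3% | −6% | −9% |
|---|---|---|---|---|---|---|
| swelling needed | 6.8% | 3.8% | 0.9% | 13.4% | 17.0% | 20.9% |

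For one patient with 5% swelling:

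- With 6% general gain: 1.05·1.06 − 1 = 11.3% against T0, and 5.0% between arms.
- With 6% prior asymmetry, the two results swap.

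So the ambiguity can change individual classifications. The values of d are assumptions; the protocol gives no distribution for either quantity.

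**3. What it does to the group comparison.** If a share f of patients without lymphedema is counted in both groups, and a share Se of true cases is found in both, the observed difference is (Se − f)·(P1 − P2). It is zero when the true difference is zero, so common misclassification produces no false benefit; it dilutes. With Se = 1 and 44 per group (uncorrected test):

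| f (assumed) | observed proportions | power |
|---|---|---|
| 0 | 30.0% vs 5.0% | 88% |
| 2% | 31.4% vs 6.9% | 84% |
| 5% | 33.5% vs 9.75% | 78% |
| 10% | 37.0% vs 14.5% | 68% |

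**4. Would a T0-corrected ratio be better?** The candidate is (A_t/U_t)/(A_0/U_0) − 1 ≥ 0.10, with A the affected and U the unaffected arm. It removes both general change and prior asymmetry but carries four tape errors instead of two. On the log scale, with tape-error SD s per arm, the error variance is 4s² for the ratio and 2s² + SD²(asymmetry) for the raw between-arm rule. The ratio is less noisy only if the asymmetry SD exceeds √2·s, that is 1.4% at s = 1% and 2.8% at s = 2%.

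Simulation with assumed inputs, patients at or above 10% at T0 excluded:

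| tape SD | asymmetry mean, SD | false events: raw / ratio | true 12% swellings found: raw / ratio |
|---|---|---|---|
| 1% | 0, 2% | 0.0% / 0.0% | 76.7% / 81.5% |
| 1% | 2%, 4% | 1.4% / 0.0% | 80.8% / 82.2% |
| 2% | 0, 2% | 0.3% / 0.9% | 69.6% / 67.6% |
| 2% | 0, 3% | 0.8% / 0.9% | 66.3% / 67.9% |
| 2% | 0, 4% | 1.7% / 0.9% | 63.3% / 68.3% |
| 2% | 2%, 2% | 1.3% / 0.9% | 86.1% / 68.2% |
| 2% | 2%, 4% | 3.9% / 0.9% | 76.7% / 69.4% |

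Neither rule wins throughout. The raw rule would lose sensitivity if mean asymmetry ran the other way, with the affected arm smaller, which these rows do not cover. The same-arm rule gave false events between about 0.15% and 8.8%, the upper end at an assumed general gain of mean 2%, SD 5%.

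**The case for a change.** The strongest case for a change is that this is the sole primary outcome, that the protocol itself fixes the definition, and that it does so incompletely. Which arm is taped at which visit is a measurement rule, and a later analysis plan cannot create readings that were never taken. Citing a society's rule does not help a reader if the comparator is left out when the rule is restated.

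The omission stands: no section names the comparator or says that the unaffected arm is taped. The harm is not shown. The same-arm reading is inferred from the section heading, which says where edema is assessed; section 3.2.1 mentions neither T0 nor a change over time. Common misclassification dilutes the contrast but does not favour either group, and the equal-error condition is plausible under one method and collectors described as unaware of grouping. It would be weaker under the same-arm reading if the exercise program itself altered limb volume, but the protocol gives nothing from which to judge that.

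The practical room is also small. With 97 patients already through the study, a T0 reading of the unaffected arm that was not taken cannot be recovered.

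**Conclusion.** The comparator is unwritten, but no change to the plan follows. A between-arm comparison is at least as natural a reading as any other, and applied at every visit it gives a sound group comparison. The only substantive alternative, the T0-corrected ratio, is a trade-off: at 2% tape error its false events range from 0.6 points more to 3.0 points fewer than the raw rule's, and its detection of true 12% swellings from 5 points better to 18 points worse.

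This rests on three assumptions: one comparator was used throughout, misclassification is alike in both groups, and the tape-error and asymmetry values lie in the ranges tried. None of those values is in the protocol, so the true size of the dilution cannot be given. What remains is a matter of reporting: the trial report should name the comparator that was used.
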